2.3 RISK/BENEFIT ASSESSMENT

2.3.1 KNOWN POTENTIAL RISKS

Table 4. Predicted COHb levels in ARDS.

| CO (ppm) | 10 min | 20 min | 30 min | 40 min | 50 min | 60 min | 90 min | 120 min |
|----------|--------|--------|--------|--------|--------|--------|--------|---------|
| 200 | 1.2 | 1.6 | 2.0 | 2.3 | 2.7 | 3.0 | 3.8 | 4.5 |
| 300 | 1.4 | 2.1 | 2.6 | 3.2 | 3.7 | 4.2 | 5.4 | 6.5 |
| 400 | 1.7 | 2.5 | 3.3 | 4.0 | 4.7 | 5.3 | 7.0 | 8.4 |
| 500 | 1.9 | 2.9 | 3.9 | 4.8 | 5.7 | 6.5 | 8.6 | 10.3 |
| 600 | 2.1 | 3.4 | 4.6 | 5.7 | 6.7 | 7.7 | 10.2 | 12.2 |
| 1000 | 3.0 | 5.2 | 7.1 | 9.0 | 10.7 | 12.3 | 16.3 | 19.4 |

Mean ARDS values: $DLCO$ 3.45 mL/min/mmHg, V_A 4.35 L/min, weight 77.1 kg, Hgb 8.5 g/dL, FiO_2 0.6.

Potential risks of active study drug include headache and tachycardia. In cases of overdose, patients can have nausea, vomiting, seizures, problems thinking, coma, cardiopulmonary arrest, and death. These adverse effects are seen at doses much higher than those proposed in this study. Subjects will be vigilantly monitored for side effects during study drug administration and COHb and lactate levels will be carefully monitored throughout the study. There may be other risks of iCO in patients with ARDS that are currently unknown. Subjects will be monitored closely throughout their participation in the trial. In our recently completed Phase I trial, no protocol-specified iCO administration-related AEs occurred in 12 subjects, and the Data and Safety Monitoring Board (DSMB) has recommended moving forward with Phase Ib and Phase II studies after three interim analyses.

Although there is a risk of toxicity associated with inhalation of high concentrations of CO, low dose iCO has been shown to be protective in animal models and safe in human subjects. Data from animal studies demonstrate that iCO has beneficial effects on outcomes in sepsis and ALI. Furthermore, extensive data is available regarding the safety and tolerability of low dose iCO in healthy volunteers and more recently, in subjects with COPD and IPF. Subjects enrolled in the study will receive the same standard of care that is otherwise available to non-study patients in an ICU setting.

Risks of blood draws

All subjects will have blood drawn for research purposes. Most blood will be drawn through existing indwelling catheters. Risks of drawing blood percutaneously are uncommon and include bleeding and bruising.

Risks of radiation exposure

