9.2 SAMPLE SIZE DETERMINATION

As the primary endpoint of this Phase Ib trial is safety, this sample size of 36 (2:1 CO:placebo) was chosen based on a probability to estimate the mean difference between measured and predicted COHb levels in the CO group within 0.5% with 95% confidence to support the accuracy of the CFK equation.

Our preliminary data from our Phase Ia trial demonstrate that the CFK equation is highly accurate at predicting COHb levels following a 20 minute exposure to 200 ppm iCO ($r=0.916$, $R^2=0.9204$; $p<0.0001$). The mean difference between measured and predicted COHb levels was 0.1467 ± 0.2738 . Using a more conservative estimate of standard deviation (SD)=0.6, we will have >99% probability that 95% confidence intervals around the mean difference between measured and predicted COHb levels will be -0.353% to 0.647%. Our calculation includes an 8% dropout rate.

The goal of the safety evaluation for this study is to identify safety concerns associated with CO administration. The ability of the study to detect administration-related AEs or SAEs can be expressed by the true event rate above which at least one SAE would likely be observed and the true event rate below which no events would likely be observed. Specifically, for the CO arm of the study (n=24), there is a 90% probability of observing at least one AE if the true background rate of that AE is 10% and a 97% probability of observing at least one AE if the true background rate of that AE is 15%. For the placebo arm of the study (n=12), there is an 83% probability of observing at least one AE if the true background rate of that AE is 15% and a 91% probability of observing at least one AE if the true background rate of that AE is 20%. In our Phase Ia trial, there were no administration-related AEs and no SAEs related to study product or procedures.

Probabilities of observing one or more events between the groups are presented in **Table 6** below for a range of possible true AE rates. These calculations provide a more complete picture of the sensitivity of this study design to identify potential safety problems with CO.

Table 6. Probability of observing 1 or more events between the groups for different true AE rates

| CO group | | | Placebo Group | | |
|----------|--------------|-----------------------------|---------------|--------------|-----------------------------|
| n | True AE rate | Power to detect ≥ 1 AE | N | True AE rate | Power to detect ≥ 1 AE |

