9.4.3 ANALYSIS OF THE SECONDARY ENDPOINT(S)

We also hypothesize that iCO will reduce the severity of ARDS as measured by lung injury score (LIS), $\text{PaO}_2/\text{FiO}_2$, oxygenation index (OI), and dead space fraction (Vd/Vt). These endpoints will be analyzed using repeated measures analysis of covariance (ANCOVA) to assess the effects of treatment, time, and the interaction between time and treatment, while incorporating between-patient variation in baseline measurements and important covariates including smoking, age, sex, and severity of ARDS. Age and sex will be considered as important biological variables in all analyses.

Interaction contrasts will include polynomial trends across time, focusing on a linear trend suggesting improvement and a quadratic trend suggesting that improvement is leveling off. As part of our analysis, we will also include the interaction between treatment and entry criteria (ARDS/Sepsis vs. Non-ARDS/Sepsis Pneumonia vs. Non-ARDS/non-Sepsis Pneumonia) in the model. Because the study is not powered for the interaction between treatment and entry criteria, that test will be exploratory. We will also perform post-hoc analyses within each criteria group to generate hypotheses for future study.

With 24 subjects in the CO group and 12 subjects in the placebo arm, we will have 80% power ($\alpha=0.05$) to detect a 0.95 difference in LIS between treatment arms, assuming a conservative SD of 0.8 (**Table 7**). We will also have 80% power to detect a 78.6 mm Hg difference in $\text{PaO}_2/\text{FiO}_2$, a 12.0 difference in OI, and a 0.14 difference in Vd/Vt between treatment arms, assuming SDs of 66, 10.1, and 0.12 respectively.

Table 7. Minimal detectable difference at 80% power.

| Endpoint | SD | Detectable Difference ($\alpha= 0.05$) |
|-----------------------------|-----|--|
| LIS | 0.8 | 0.95 |
| $\text{PaO}_2/\text{FiO}_2$ | 66 | 78.6 |

| Endpoint | SD | Detectable Difference ($\alpha= 0.05$) |
|----------|------|---|
| OI | 10.1 | 12.0 |
| Vd/Vt | 0.12 | 0.14 |

Ventilator-free days (VFDs), hospital- and ICU-free days, and Sequential Organ Failure Assessment (SOFA) scores will each be analyzed separately using ANCOVA with treatment arm as the main effect. Given our modest sample size, we will only be powered to see large changes.

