Results from the Hayling Sentence Completion Test and Montreal Cognitive Assessment (MoCA) testing will be compared between CO and placebo groups using the Mann-Whitney U test or t-test (if normally distributed). If significantly different between the groups, scores from the Hayling Sentence Completion Test and MoCA testing may be incorporated into exploratory multiple regression analyses.

Mortality will be analyzed using Cox regression models for time-to-death with treatment arm as the main predictor, and with important covariates including smoking, age, and sex in the model. Hazard ratio (HR) and 95% CI for CO relative to placebo will be reported, along with Kaplan-Meier plots and estimated proportions surviving at 28, 60, and 180 days.

To address potential bias from unobserved study outcomes due to missed visits, premature withdrawal, or death and to ensure robust data analyses, we will work closely with [name] at Johns Hopkins University, who has extensive expertise with long-term outcomes assessment after acute respiratory failure and critical illness. [name] will provide his expertise and assist with statistical methods developed by his Outcomes After Critical Illness and Surgery (OACIS) Group to address missing data and assess long-term outcomes that may be “truncated due to death”. We will use the statistical software application developed by his group using R and Shiny to impute missing data among survivors given the high mortality in ARDS. We will also employ other statistical approaches used by his OACIS Group to assess long-term outcomes in critically ill patients. These include a composite endpoint approach using both functional outcome and survival, as well as other statistical methods (e.g. survivors only analyses and survivor average causal effect [SACE]).

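### Late neurocognitive scores get an unadjusted test, with regression allowed only after significance, and no adjusted estimate or confidence interval is planned

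*Combined protocol and SAP*

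**What the plan says.** Neurocognitive function at 3 and 6 months is the tenth secondary endpoint (Sections 1.1, 3 and 9.1). The Schedule of Activities places MoCA-BLIND and Hayling at those two visits only, so there is no baseline score.

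For the analysis, Section 9.4.3 names a two-group Mann-Whitney U test, or a t-test if the scores are normal, and continues: "If significantly different between the groups, scores from the Hayling Sentence Completion Test and MoCA testing may be incorporated into exploratory multiple regression analyses". It gives no confidence interval, margin, SD or detectable difference for these scores.

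Earlier in the same section: "Age and sex will be considered as important biological variables in all analyses". The lung-physiology endpoints get repeated-measures ANCOVA with smoking, age, sex and ARDS severity. Mortality gets a Cox model with smoking, age and sex, and the hazard ratio with 95% CI is reported without any condition on its p-value.

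For missed visits and deaths, Section 9.4.3 lists imputation among survivors, a composite with survival, survivors-only analyses and the survivor average causal effect (SACE).

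Section 2.3.1 says that in overdose "patients can have nausea, vomiting, seizures, problems thinking, coma, cardiopulmonary arrest, and death", and adds that these effects occur at doses much higher than those proposed here.

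**The concern.** Two things look wrong.

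First, the cognition sentence departs from the section's own rule on age and sex. Nothing in the design balances age: randomisation is unstratified (Section 6.3), and 36 patients are split 2:1. With no baseline score, age is an obvious available predictor.

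Second, a model beyond the two-group test is considered only when that test is significant, and even then it is optional and exploratory. For a measure that also serves safety, the non-significant case is the one where a reader most needs an estimate and an interval, to see how large a deficit remains possible. Routine adverse-event collection stops at day 7 unless an event is judged related (Section 8.7.5), so these tests carry most of the late non-fatal information.

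The practical risk is that a non-significant p-value is read as reassurance. Section 2.2.5 already cites the absence of significant neurocognitive differences in two previous studies when it argues that inhaled CO is well tolerated.

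**Working it through.** **The plan's own figures.** None exists for cognition. The nearest is Table 7: "With 24 subjects in the CO group and 12 subjects in the placebo arm", 80% power at alpha 0.05 for a 0.95 difference in LIS with SD 0.8, which is 0.95 / 0.8 = 1.19 SD. A two-sided two-sample t-test at 24/12 gives 1.02 SD, or 1.02 × 0.8 = 0.82, and power at 0.95 is 0.90. Table 7 therefore does not reproduce from its stated inputs. It errs on the cautious side, and I do not use it below.

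**Inputs.**
- Arms 24 and 12 (Section 9.4.3).
- Alpha 0.05. Sidedness is not stated, so two-sided is assumed.
- Deficit of 1 SD: assumed.
- Number tested: not given. Section 9.4.3 says only that ARDS mortality is high. Section 9.2 says "Our calculation includes an 8% dropout rate", but of the COHb calculation; 36 × 0.92 is about 33, or 22/11. I take 36 down to 18 tested, kept at 2:1.

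**Formulas, in SD units.** SE = √(1/n₁ + 1/n₂). Noncentrality = 1/SE. Power = P(noncentral t > t₀.₉₇₅ on n₁ + n₂ − 2 df). Half-width of the 95% CI = t₀.₉₇₅ × SE.

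| Tested (CO/placebo) | SE | t₀.₉₇₅ | 1/SE | Power | Missed | CI half-width |
|---|---|---|---|---|---|---|
| 24/12 | 0.354 | 2.032 | 2.83 | 0.785 | 21.5% | 0.72 SD |
| 22/11 | 0.369 | 2.040 | 2.71 | 0.746 | 25% | 0.75 SD |
| 18/9 | 0.408 | 2.060 | 2.45 | 0.653 | 35% | 0.84 SD |
| 14/7 | 0.463 | 2.093 | 2.16 | 0.536 | 46% | 0.97 SD |
| 12/6 | 0.500 | 2.120 | 2.00 | 0.468 | 53% | 1.06 SD |

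Mann-Whitney does slightly worse in simulation: 0.76 at 24/12, 0.49 at 14/7 and 0.40 at 12/6. All figures are for one score at one visit.

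**What age adjustment buys.** I simulated a linear model with arm and age (12,000 runs per setting, normal data), which allows for chance age imbalance.

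| Assumed age-score correlation | Gain in power, 24/12 to 12/6 | Narrower 95% CI |
|---|---|---|
| 0.3 | 1 to 3 points | 1% to 3% |
| 0.5 | 9 to 10 points | 10% to 12% |

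A formula that ignores chance imbalance puts the gain at correlation 0.5 at 11 to 12 points (0.65 to 0.77 at 18/9; 0.47 to 0.58 at 12/6). Overall this is about 1 to 12 points. Adding sex, assumed unrelated to the score, ranges from a loss of about 1 to 3 points (18 to 21 tested, correlation 0.3) to a gain of about 9.

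**The case against.** A reader might infer that a 1-SD harm would be declared absent about half the time because of the missing adjustment and the significance condition. The documents do not support that reading:

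- The condition applies after the first test and cannot alter its power. The miss rate comes mainly from the number tested, and an adjusted analysis also misses many such deficits.
- About half holds only near 12/6 to 14/7 tested. If all 36 are tested, the figure is about 21%.
- The figure is per comparison, and there are four (two scores, two visits). If all four carried a 1-SD deficit, the chance that at least one is significant is 0.77 to 0.89 at 14/7, assuming correlations of 0.3 to 0.7 between them. With no effect that chance is still 0.13 to 0.18, and no multiplicity rule is given.
- In a randomised comparison, omitting age costs precision and does not cause systematic bias. Selection by survival is a separate matter, which age adjustment does not remove.
- Cognition is not the only late check on a named harm. Death is on the same list, and survival is modelled with estimates to 180 days. Related adverse events after day 7 remain reportable.
- The plan nowhere says that a non-significant result will be reported as no effect.
- The conditional regression is loosely described. The text does not say whether the scores would be outcome or predictor, so it cannot be assumed to be the model that corrects for age.

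All of this stands. The planned composite, SACE and imputation methods also carry no significance condition, and Section 9.4.3 concedes of other secondary endpoints: "Given our modest sample size, we will only be powered to see large changes". None of it supplies an age-adjusted difference with an interval for these scores, or removes the conflict within Section 9.4.3.

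**Conclusion.** The concern holds in a limited form. Section 9.4.3 contradicts itself on age and sex for the cognitive scores, and makes any regression optional and dependent on significance. It therefore plans no adjusted estimate or interval for the only scheduled late non-fatal measure of a named overdose harm.

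Under the assumed 36 down to 18 tested, one comparison misses a 1-SD deficit about 21% to 53% of the time. The interval extends about 0.7 to 1.05 SD either side of the estimate, so at 14/7 an observed difference of zero is still compatible with a deficit of nearly 1 SD. A p-value alone would not show that. These sizes rest on the assumed number tested, the 1-SD effect and two-sided alpha 0.05.

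The main benefit of the change is that the interval is reported; the gain in precision is modest. This is a worthwhile correction to one secondary endpoint. It does not show that the trial would conceal harm.

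**What to change.** In Section 9.4.3, delete the sentence that makes regression conditional on significance. In its place:

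1. For MoCA-BLIND and Hayling, at 3 and at 6 months, report the iCO-minus-placebo difference with 95% CI from a linear model with arm and age, whatever the p-value. Use ranked scores if the distribution is skewed, and note that the interval is then in ranks.
2. Add sex in a sensitivity model, so that the statement on age and sex in all analyses is met.
3. Keep the raw Mann-Whitney or t-test as support.
4. Apply the planned composite, SACE and imputation methods alongside this estimate.
5. State the number tested per arm and the largest deficit that each interval does not exclude.

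The cost is SAP wording and a few extra models. Age and sex are already collected. The statistical price is one or two degrees of freedom, and with 18 to 27 tested, adding sex can cancel the gain if the age-score correlation is near 0.3. That is why sex belongs in the sensitivity model.

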1.4 DEFINITIONS

Acute Kidney Injury: Acute kidney injury network Stage 3 disease, defined as a threefold increase in creatinine from baseline or the need for dialysis

Completing 48 hours of UAB (from weaning form): Defined as the date (calendar day) that the subject reaches exactly 48 hours of UAB. Example: if subject meets UAB at 1900 on 6/1/06 and does not return to AB, then the date of completing 48 hours of UAB would be 6/3/06.

Date of first UAB (from Study Termination form): Defined as the first day that the subject is on UAB from midnight to midnight. Example: if subject meets UAB at 1900 on 6/1/06, then the date of first UAB would be 6/2/06, as long as subject does not return to AB on 6/2/06.

Day zero: Defined as day of randomization. Study days are calendar days.

Drug held/hold drug: Study medication withheld for 24 hours.

Drug permanently discontinued: Study medication stopped for remainder of the trial.

Enrollment: All randomized participants will be included in the intent-to-treat (ITT) population. All randomized subjects who receive at least one dose of study product (CO vs. placebo) will be included in the safety analyses (*ie.* modified ITT). For secondary and exploratory endpoints, subjects may also be analyzed according to the number of study drug doses completed. Because some patients may withdraw or have a change in clinical status precluding dosing of study drug (eg. post-randomization lactic acidosis), we may randomize additional patients to achieve the enrollment goal of 36 patients who are randomized and treated with at least one dose of the study drug. We expect this to be an uncommon occurrence. Patients who are randomized but do not undergo any study procedures or study treatment will not be included in the study analysis.

Extubation: Removal of an orotracheal, nasotracheal tube, or unassisted breathing with a tracheostomy.

Home: level of residence or health care facility where the patient was residing prior to hospital admission

Hospital Mortality to Day 60: This primary endpoint includes all deaths following randomization in any health care facility prior to discharge “home” until study day 60. Study subjects still in a health care facility at study day 61 are considered alive for this endpoint.

Interruption of Dosing During Drug Administration: Study medication prematurely stopped prior to 90 minutes.

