4 STUDY DESIGN

4.1 OVERALL DESIGN

This is a multi-center, randomized, partially double-blind, and placebo-controlled **Phase Ib safety clinical trial** of inhaled CO (iCO) for the treatment of pneumonia and/or sepsis-induced ARDS. We hypothesize that low dose iCO will be safe and well-tolerated and that the CFK equation-based iCO personalized dosing algorithm will be accurate in achieving a target COHb level of 6-8% in patients with pneumonia and/or sepsis-induced ARDS.

Intubated subjects (n=36) with pneumonia and/or sepsis-induced ARDS who have consented to participate will be randomized in a 2:1 ratio to treatment with iCO (n=24) or medical grade air (n=12) for 90 minutes daily for 3 consecutive days. Subjects will be administered iCO or placebo air via inhalation through the mechanical ventilator using the CO Delivery System (COeventDS, 12th Man Technologies). Subjects randomized to CO will be administered iCO at an individualized dose between 200-500 ppm as determined by a personalized iCO dosing algorithm to achieve a COHb level of 6-8%. Subjects randomized to placebo will receive medical grade air through the COeventDS from identical appearing gas cylinders. The study drug will be administered for up to 3 days following randomization or until discontinuation of mechanical ventilation, whichever occurs first. For patients who have a tracheostomy, the equivalent of extubation for the purposes of this protocol will be breathing via tracheostomy with unassisted breathing.

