Sequential Organ Failure Assessment (SOFA): The SOFA score will be calculated based on the worst values recorded in the past 24 hours. Calculation variables are described in **Appendix B5**.

- a) Worst PaO₂/FiO₂ for that date
- b) Worst creatinine (or urine output), bilirubin, and platelet count for that date
- c) Worst Glasgow Coma Scale for that date
- d) Vasopressor use and maximal dose for that date

Vasopressors and Inotropes Review: The following vasopressors/inotropes will be recorded in the study eCRFs (epinephrine, norepinephrine, phenylephrine, vasopressin, dopamine, dobutamine, phosphodiesterase inhibitors, including dose).

Ventilator Parameters: The study staff will record ventilator parameters prior to starting study drug administration. The following settings will be recorded:

- a) Mode of ventilation
- b) FiO₂ and PEEP
- c) Tidal volume, Respiratory rate (set rate and total rate), Minute ventilation, Inspiratory flow rate
- d) Peak pressure, Plateau pressure, Compliance, and Mean airway pressure. If on a pressure-cycling mode, peak pressure during inspiration will be assumed to be the plateau pressure.
- e) Pressure during inspiration if on a pressure targeted mode (PSV, PCV, etc)

Vital Signs: Heart rate (beats/min), systemic systolic, diastolic, mean arterial blood pressure (mm Hg), and body temperature (°C), will be recorded in the eCRF.

Vital Status: Vital status will be assessed at Days 28, 60, 3 months, and 6 months. Subjects who have been discharged from the hospital will be contacted by phone. Additional information will be collected on discharge status, ventilator status, and vasopressor status at Days 28 and 60.

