9 STATISTICAL CONSIDERATIONS

9.1 STATISTICAL HYPOTHESES

Hypothesis: We hypothesize that low dose iCO will be safe and well-tolerated and that the CFK equation-based iCO personalized dosing algorithm will be accurate in achieving a target COHb level of 6-8% in patients pneumonia (without ARDS and sepsis or with sepsis without ARDS criteria) and with sepsis-induced ARDS at study entry.

We further hypothesize that precision-based iCO therapy will reduce the severity of pneumonia and ARDS and organ failure by suppressing mitochondrial dysfunction, inhibiting inflammasome activation and necroptosis, and accelerating resolution of inflammation.

Primary Endpoints:

1. The primary endpoint is **safety of iCO**, defined by the incidence of pre-specified administration-related AEs and SAEs.

Administration-related SAEs are: 1) myocardial infarction; 2) stroke; 3) new onset arrhythmia requiring DC cardioversion; 4) worsening hypoxemia^{1,2}; 5) COHb \geq 10%; and 6) increase in lactate by \geq 2 mmol/L.

2. **Accuracy** of the CFK equation-based personalized iCO dosing algorithm to achieve a COHb level of 6-8%.

Secondary Endpoints:

1. Lung Injury Score (LIS) on days 1-5 and day 7
2. PaO₂/FiO₂ ratio on days 1-5 and day 7
3. Oxygenation index (OI) on days 1-5, and 7
4. Dead space fraction (Vd/Vt) on days 1-3 and day 7
5. Sequential Organ Failure Assessment (SOFA) scores on days 1-5, 7, 14, and 28
6. Ventilator-free days at day 28
7. ICU-free days at day 28
8. Hospital-free days to day 60
9. Hospital mortality to days 28 and 60
10. Neurocognitive function at 3 and 6 months

Exploratory Endpoints:

1. Plasma and urine biomarkers of mitochondrial dysfunction (mtDNA)
2. Plasma and urine biomarkers of inflammasome activation (IL-18)
3. Plasma and urine biomarkers of necroptosis (RIPK3)
4. Plasma Lipid mediators (LM) and specialized pro-resolving mediators (SPMs)

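### The only analysis named for mortality, a time-to-death model reported to Day 180, does not estimate the stated secondary endpoint of hospital mortality to Days 28 and 60

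*Combined protocol and SAP*

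**What the plan says.** Section 9.1 lists the secondary endpoint as "Hospital mortality to days 28 and 60". Section 1.4 defines the Day-60 version. It "includes all deaths following randomization in any health care facility prior to discharge" home, until study day 60, and "Study subjects still in a health care facility at study day 61 are considered alive for this endpoint". There is no separate Day-28 definition.

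Section 9.4.3 names one analysis: "Mortality will be analyzed using Cox regression models for time-to-death with treatment arm as the main predictor", "with important covariates including smoking, age, and sex in the model". The outputs are a hazard ratio with 95% CI, Kaplan-Meier plots and "estimated proportions surviving at 28, 60, and 180 days". The paragraph does not define the event, does not say how discharge home is handled, and gives no censoring time. Section 8.1 adds that "Vital status will be assessed at Days 28, 60, 3 months, and 6 months", by telephone for patients who have left hospital.

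Two other places bear on this. Section 9.4.1 has a general rule that categorical outcomes are compared between arms by chi-square or Fisher's exact test, without naming hospital mortality. Section 9.4.4 uses 28- and 60-day hospital mortality as outcomes in the biomarker analyses.

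**The concern.** The endpoint is a yes/no outcome at a fixed day, with a place-of-death condition. Every randomized patient stays in the denominator, and anyone who has gone home counts as alive. The named analysis is a time-to-event model whose horizon runs three times past Day 60 and which is not tied to that definition.

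Two things are at stake. The number reported as the mortality result may not be the endpoint the protocol lists. And because event and censoring are not fixed in advance, the choice between quite different numbers stays open until the data are in hand.

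**Working it through.** The plan gives no mortality rate, expected number of deaths, target hazard ratio or power for mortality, so there is no figure of its own to reproduce.

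**Inputs.** 36 patients, 24 iCO and 12 placebo (4.1). At least four model terms: treatment, smoking, age and sex (9.4.3; the covariate list is open-ended). Mortality of 20% to 40% is an assumption.

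**Step 1. Classify the same patients under each rule.**

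| Patient | Endpoint (1.4) | Time-to-death, all-cause | Time-to-death, censored at discharge home |
|---|---|---|---|
| Dies in ICU, Day 10 | Death | Event | Event |
| Home Day 20, dies at home Day 40 | Alive | Event, Day 40 | Censored, Day 20 |
| Home Day 20, alive at Day 60 | Alive, in denominator | At risk to Day 60 | Censored, Day 20 |
| Still in a facility, dies Day 70 | Alive | Event, Day 70 | Event, Day 70 |

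Only the first row agrees throughout. The Day-70 death does not affect a Kaplan-Meier proportion at Day 60, but it enters the hazard ratio and the Day-180 proportion.

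**Step 2. Size under the all-cause reading.** The documents do not allow an estimate of how many deaths would be classified differently. Each death at home before Day 60 moves the arm's crude proportion by 1/24 = 4.2 percentage points (iCO) or 1/12 = 8.3 points (placebo).

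**Step 3. Size under censoring at discharge home (hypothetical).** Of 36 patients, 6 die, then 22 go home, then 2 of the remaining 8 die in a facility before Day 60.
- As defined: (6 + 2)/36 = 22%.
- Kaplan-Meier with discharge home censored: 1 − (30/36) × (6/8) = 37.5%.

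The gap arises because Kaplan-Meier assumes the discharged patients would have gone on dying at the rate of those still in a facility, while the definition keeps them as alive.

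**Step 4. Precision of the named model.** Deaths D = 36 × rate. Deaths per term = D/4. The unadjusted 95% CI for the hazard ratio runs from the estimate divided by f to the estimate times f, where f = exp(1.96 × √(1/(D × 2/3 × 1/3))).

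| Assumed mortality | D | Per term | f |
|---|---|---|---|
| 20% | 7.2 | 1.8 | 4.7 |
| 30% | 10.8 | 2.7 | 3.5 |
| 40% | 14.4 | 3.6 | 3.0 |

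A simulation of the four-term Cox model with no treatment effect (24:12, 1,000 runs per rate) gave no usable estimate in 14%, 3% and 0.4% of trials at 20%, 30% and 40% mortality. Type I error among the fits that could be estimated was 4% to 5%, so not inflated.

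**Step 5. Precision of the endpoint as defined.** With an assumed 30% in both arms, the half-width of the risk-difference 95% CI is 1.96 × √(0.21/12 + 0.21/24) = 0.32, or about ±32 percentage points (normal approximation). For an assumed 40% against 20%, the pooled normal formula gives about 26% power, and an exact test would generally give less.

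**The case against.** A reader might infer that no analysis of the binary endpoint is planned and that it will go unreported. The documents do not support that. The chi-square or Fisher rule in 9.4.1 could cover two proportions, and 9.4.4 shows that the hospital-mortality variable will be derived. What remains is that the mortality paragraph does not invoke the rule, and the rule yields a test without a risk difference or interval.

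A reader might also take it as stated that the Cox model counts every death. Section 9.4.3 says only time to death. All-cause is an inference, though a strong one: an endpoint that stops at Day 60 cannot yield a Day-180 proportion, vital status is collected after discharge, and Section 7.3 uses the National Death Index to verify survival. One could instead keep patients who go home as event-free to Day 60, and the Kaplan-Meier proportions at Days 28 and 60 would then match the definition. But the plan states no such rule, and the Day-180 output does not fit it.

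The endpoint is also wider than death in the study hospital. Deaths in another facility before going home count, so the gap from all-cause death to Day 60 may be small.

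Finally, a reader might conclude that too few deaths is the defect, or that the covariates are wrong. Few deaths is a property of 36 patients, not of Cox regression, and Step 5 shows that the binary analysis is imprecise too. The plan claims no power for mortality, and 9.4.3 concedes, for the free-day and SOFA endpoints, that only large changes are detectable. It also commits to considering age and sex in all analyses, so dropping them is a trade-off. These objections stand.

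**Conclusion.** The mismatch holds on the text. Under the all-cause reading, and equally under censoring at discharge home, the hazard ratio and the survival proportions answer a different question from the listed endpoint, and the plan does not say which reading applies.

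The size in real data cannot be derived from the documents. It depends on how many patients die at home before Day 60 or anywhere after it, or, under the other reading, on how many go home early. The 22% against 37.5% in Step 3 is an illustration, not a forecast.

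The precision figures rest on assumed mortality and support only a secondary remark: at about 7 to 14 deaths, an adjusted hazard ratio is pre-specified with no fallback should it prove inestimable. This is one of ten secondary endpoints in a Phase Ib safety trial. The point should be corrected, but it does not touch the primary endpoints.

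**What to change.** In Section 9.4.3:

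1. For Days 28 and 60, report the number and proportion of deaths per arm that meet the Section 1.4 definition, with the risk difference and an exact or score 95% CI. If a test is wanted, name Fisher's exact test and refer to 9.4.1.
2. Keep the Cox and Kaplan-Meier analysis to Day 180 as a separate, supportive analysis, labelled all-cause death, with its event, time origin and censoring rule stated.
3. Optional: show the unadjusted hazard ratio beside the adjusted one, or name a fallback if the adjusted model cannot be estimated. Retaining age and sex is consistent with the plan's own commitment.

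In Section 1.4, extend the definition explicitly to Day 28, and correct its label: it calls this outcome a primary endpoint, while the synopsis and Sections 3 and 9.1 list it as secondary.

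The cost is wording. Vital status and discharge status at Days 28 and 60 are already collected (8.1). The team should confirm that, for patients moved to another facility, the case report form shows whether death came before discharge home. The change aligns analysis with endpoint; it does not improve precision.
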